97 be encouraged to take inhalations as frequently and deeply as they feel is necessary to achieve nausea relief. If a subject
98 is unable to or prefers assistance with nasal inhalation or oral solution consumption, the patient's nurse will provide any
99 assistance needed. The investigator will remain at arm's length from the patient at all times to avoid detecting prep pad
100 scent. Additionally, investigators will also instruct subjects to avoid any behavior or actions during the study that would
101 indicate which preparation pad is being used. Examples of behavior to avoid would be verbally describing the scent of the
102 preparation pad or taste of the oral solution.
103

104 The investigators will record their findings on data collection forms. The primary outcome will be nausea as measured on
105 a 10 cm visual analogue scale (VAS) at 30 minutes. This time horizon was selected as ondansetron's labeled use is
106 administration 30 minutes prior to receipt of chemotherapy to treat chemotherapy-related nausea. Nausea measurements
107 will also be collected at 10, 20, 40, 50, and 60 minutes, and then every hour up to 5 hours, then at disposition at which
108 time the patient will provide one final nausea VAS score. The study team member will not be present in the patient's room
109 during the intervals between these evaluations. At the time of each nausea measurement, patients will be offered another
110 preparation pad (up to ten pads). We will notify the patient's treating provider to prompt consideration for treatment with a
111 rescue anti-emetic (such as metoclopramide or promethazine) if the patient vomits or if the patient requests an anti-emetic
112 at any time. At the time of each nausea measurement, a pain score will also be measured on a 10 cm VAS. At the time
113 of final disposition, the patient will provide a satisfaction score on a 10-cm VAS and be asked to indicate his/her belief as
114 to whether the pad was a treatment or placebo and whether the oral solution was a treatment or placebo. Similarly, at

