49 consent, the subject's nausea and pain levels will be recorded initially. For the oral solution, they will be instructed to
50 swallow the oral solution. Receipt of oral solution (ondansetron or placebo) should occur prior to pad inhalation to be
51 followed within 5 minutes by initiation of inhalations from the allocated study pad (normal saline or ISO). For the
52 preparation pads, patients will be instructed to hold the pad approximately 1 inch from their nares and take deep nasal
53 inhalations as needed for nausea relief. Initiation of inhalations will mark time 0 for the study. If a subject is unable to or
54 prefers assistance with either nasal inhalation or oral solution consumption, the patient's nurse will provide any assistance
55 needed. The investigator will remain at arm's length from the patient at all times to avoid detecting prep pad scent.
56 Additionally, investigators will also instruct subjects to avoid any behavior or actions during the study that would indicate
57 which intervention is being used. Examples of behavior to avoid would be verbally describing the scent of the preparation
58 pad or taste of the oral solution. Investigators will not inform subjects which substances are being tested. The
59 preparation pads are commercially prepared single-use pads of ISO for the ISO + oral placebo and the ISO + oral
60 ondansetron study groups and commercially prepared single-use saline pads for the inhaled saline + ondansetron oral
61 solution group that are identical with the exception of the labeling. Both pads will remain in their original packaging. Pain
62 and nausea measurements will be gathered at 0, 10, 20, 30, and 60 minutes and then again hourly up to 5 hours, and
63 then finally at the time the patient's attending physician makes a disposition decision. The patient may withdraw from the
64 study at any time. At any time during the study, a rescue antiemetic drug can be considered by subject request or
65 provider preference. The individual pads will be de-identified, utilizing brown tape over original packaging that tears open

70 with packing as not to reveal manufacturer's labeling. The oral solution packaging will similarly be de-identified. The only
71 scenarios in which a study team member will prompt a provider to consider a rescue anti-emetic is if the patient vomits or
72 if the patient actively requests an alternative medication. A study data form will be completed for each subject by the

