43 with any other symptoms (i.e. pain) will be recorded on the CRF. This information will be self-reported by the subject.
44 -Pertinent Personal Medical/Surgical History will be recorded on the CRF. This information will be self-reported by the
45 subject.
46 -Current medications, supplements being taken and any allergies will be recorded on the CRF.
47 -Level of nausea, episodes of vomiting, pain level, adverse events, use of antiemetic medication at the 0, 10, 20, 30, and 60
48 minutes, then hourly up to 5 hours and finally at the time of patient disposition will be recorded on the CRF. Satisfaction level
49 will be recorded at study conclusion (time of patient disposition) on a VAS. This information will be self-reported by the
50 subject.
51 -Numbers of episodes of vomiting (discrete episodes separated by 120 seconds) will be recorded on the CRF as reported by
52 the patient or the patient's treating nurse.
53 -Time and doses for all drugs and fluids administered in the ED will be recorded on the CRF.
54 -Clinical impression at the time of patient disposition decision will be recorded on the CRF.
55 -Time of patient disposition decision made by attending physician will be recorded on the CRF.
56 -Any adverse events will be recorded on the CRF.
57 -Patient, provider, and study investigator perceptions of pad and oral solution contents will be recorded on the CRF.

58
59 **7.3.3. Human Biological Specimens/Tissue/Data Banking.** Not applicable.
60

61 **7.4 Statistical Consideration**

62
63 **7.4.1 Sample Size Estimation.**

64 **We expect the standard deviation of the change in baseline to 30 minute VAS scores to be approximately 28.7.¹⁷ We**
65 **define a clinically significant difference as 20 mm on the VAS.¹⁸ Given alpha = 0.025 (reflecting a Bonferonni**
66 **correction for testing of two hypotheses) and beta = 0.2 with two-tailed testing, we estimate we will require 40**
67 **patients per arm.**
68

Estimate Required Sample Size	120
Estimate Participant Drop Out / Withdrawal	60
Total Enrollment Requirement	180

69

Enrollment at Each Site	
SAMMC	180

70
71 **7.4.2 Primary (i.e., primary outcome variables) and secondary endpoints.** Primary outcome is nausea VAS measurement
72 at 30 minutes. Secondary outcomes include nausea VAS measurement at study disposition (the time at which the patient
73 leaves the ED), receipt of rescue anti-emetics, time to disposition, and patient satisfaction.
74

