75 **7.4.3 Data analysis.** In this study, the primary outcome will be evaluated using a two-tailed independent sample student t test.
76 The primary outcome will further be evaluated using a multiple regression model. For secondary outcomes, scale data will be
77 compared using a two-tailed independent sample student t test while categorical data will be compared using a chi-squared
78 test.
79

80 **7.7 Confidentiality.**

31 Protection of Data. Subjects will be assigned a study number upon enrollment in order to facilitate subsequent removal of
32 identifiers upon completion of data analysis. The study number will be recorded on the data collection form and on a study
33 key, which links the study number with the subject's name, FMP, SSN, and DOB. Otherwise patients will be de-identified by
34 eliminating names and collecting only demographic (with ages greater than 89 categorized as "greater than 89"), general
35 description of chief complaint, personal medical, surgical, and medication history; and any other information specific to
36 inclusion and exclusion criteria. The case report forms, signed consent forms, and signed HIPAA authorizations will be stored
37 in a locked cabinet only accessible to the study investigators within the secure EM APD-R office.

38
39 **7.7.1 Certificate of Confidentiality.** N/A.

40 41 **8.0 RISKS/BENEFITS ASSESSMENT**

42
43 **8.1 Risks.** There is a risk to the subjects related to loss of confidentiality. However, this risk is minimized by using a
44 unique study code while collecting study data and limiting access to subject records to the study team. Since all patients
45 will be receiving treatment for nausea (either inhaled isopropyl alcohol, oral ondansetron, or both), we believe the risks of
46 delay in treatment or symptom relief are minimal. Nevertheless, if the treatment to which subjects are allocated is not
47 effective in treating their symptoms, they may experience a delay in rescue therapy and so a delay in symptom relief. We
48 seek to minimize this risk by permitting, subjects to request an antiemetic at any time and to withdraw from the study at
49 any time.

50
51 Additionally, there may be an extremely rare incident of a subject that may have a sensitivity to inhaling ISO. The
52 exclusion criteria were defined to minimize the risks of such reactions by excluding patients recently exposed to
53 medications such as cefoperazone, disulfiram, or metronidazole.

54

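### The sample size rests on the SD of the change from baseline, but the primary t test compares raw 30-minute VAS scores, so the stated 80% power does not describe the planned test

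*Combined protocol and SAP*

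**What the plan says.** - **Section 7.4.1 (sample size):** "We expect the standard deviation of the change in baseline to 30 minute VAS scores to be approximately 28.7". With a 20 mm difference, two-sided alpha of 0.025 and beta of 0.2, this leads to 40 per arm, or 120. The enrolment table adds 60 under "Estimate Participant Drop Out / Withdrawal", for a total of 180.
- **Section 6 (research design):** "The primary outcome will be nausea as measured on" a 10 cm VAS at 30 minutes.
- **Section 7.4.2 (endpoints):** "Primary outcome is nausea VAS measurement" at 30 minutes. Neither section mentions change from baseline.
- **Section 7.4.3 (data analysis):** "the primary outcome will be evaluated using a two-tailed independent sample student t test". It adds: "The primary outcome will further be evaluated using a multiple regression model". No covariates are named.
- **Section 7.3 (procedures):** after consent, "nausea and pain levels will be recorded initially", with no instrument named. "Receipt of oral solution (ondansetron or placebo) should occur prior to pad inhalation", and time 0 is the start of inhalation. The schedule table puts the first nausea VAS at 0 minutes, in the column where the patient drinks the solution and starts inhaling.
- **Section 7.3.2 (data collection):** initial nausea is the screening verbal score (VNRS). Level of nausea at 0 minutes is listed separately.

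**The concern.** The variable used to size the trial (change) is not the variable tested (30-minute score). Their SDs differ unless the baseline SD and the baseline-to-30-minute correlation happen to make them equal, and the plan gives neither. The power statement therefore cannot be checked for the planned test.

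The added regression does not close the gap. It is supplementary, and nothing says that baseline nausea is in it. With no covariates named, the adjusted result also depends on choices that could be made after the data are seen.

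Any repair that uses baseline needs a defined baseline. As written, the first VAS could be marked before or after the oral solution.

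**Working it through.** **Inputs from section 7.4.1:** difference 20 mm, change SD 28.7 mm, two-sided alpha 0.025, power 80%, 40 per arm.

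**Step 1. Reproduce the plan's figure.**
Normal formula: n = 2 × [(2.2414 + 0.8416) × 28.7 / 20]² = 39.15, which rounds up to 40. Noncentral t: 79.5% power at 40 per arm and 80.6% at 41. The stated 40 is therefore correct for a t test on *change scores*.

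**Step 2. What the raw-score test needs.**
Solving noncentral-t power = 80% for the 30-minute SD gives 28.54 mm at 40 per arm and 35.15 mm at 60 per arm (all 180 retained).

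**Step 3. Link the two SDs.**
Let c be the change SD, s0 the baseline SD, s1 the 30-minute SD and ρ the correlation:

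c² = s0² + s1² − 2ρ·s0·s1

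so s1 = ρ·s0 + √[c² − s0²(1 − ρ²)]. If s0 = s1, then s1 = c/√[2(1 − ρ)].

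The plan gives neither s0 nor ρ, so both are **assumptions**. Two settings were used:
- s0 = 20.2 mm, the SD of a uniform distribution over 30–100 mm (70/√12). This treats the VAS as tracking the entry threshold of 3 on the verbal scale.
- Equal SDs at baseline and 30 minutes.

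Worked case, s0 = 20.2 and ρ = 0.4: s1 = 0.4 × 20.2 + √(28.7² − 20.2² × 0.84) = 8.08 + √(823.69 − 342.75) = 8.08 + 21.93 = 30.0 mm.

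**Step 4. Power at 40 per arm with c = 28.7.**
The adjusted analysis uses residual SD = s1·√(1 − ρ²) and 2n − 3 degrees of freedom.

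| Setting | ρ | 30-min SD | Raw t test | Change score | Baseline-adjusted |
|---|---|---|---|---|---|
| s0 = 20.2 | 0.3 | 27.3 | 84% | 79.5% | 87% |
| s0 = 20.2 | 0.4 | 30.0 | 75.5% | 79.5% | 83% |
| Equal SDs | 0.3 | 24.3 | 92% | 79.5% | 94% |
| Equal SDs | 0.4 | 26.2 | 87% | 79.5% | 92% |
| Equal SDs | 0.5 | 28.7 | 79.5% | 79.5% | 90% |

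For s0 = 20.2, the number per arm for 80% power (raw v adjusted) is 37 v 34 at ρ = 0.3 and 45 v 38 at ρ = 0.4. Equal SDs with ρ = 0.6 would give 69% v 88%, but that needs SDs of 32 mm at both times, which is at the edge of plausibility. It is not relied on.

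Simulation of 20,000 trials agrees (raw/change/adjusted): 83.6/80.0/87.0% and 76.1/80.3/83.1% for the first two rows, and 79.8/80.1/90.1% for the last.

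**Step 5. Why adjustment fits the existing sample size.**
The residual SD is the smallest SD of (30-minute score − b × baseline) over all slopes b. The change score is the case b = 1, so the residual SD cannot exceed the change SD. In the worst case (residual SD = 28.7, variance inflated by 1 + 1/77 for chance baseline imbalance), power at 40 per arm is 78.9%.

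**Step 6. If the change SD is 10% larger (1.1 × 28.7 = 31.6).**
Change-score power is 71% and the adjusted worst case is 70%. With s0 = 20.2, raw v adjusted is 72% v 76.5% (ρ = 0.3) and 64.5% v 73% (ρ = 0.4). Adjustment helps but does not restore 80%.

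**The case against.** **No harm is demonstrated.** The t test is unbiased and keeps its type I error. In three of the five rows above the raw test exceeds 80%, in one it matches the plan, and in one it falls about 4.5 points short. That one row depends on an assumed baseline SD and correlation. This stands: underpowering is not shown.

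**Enrolment gives slack.** At a 30-minute SD of 30 mm, 45 per arm restores 80%. That is 135 of 180, so a 25% loss could be absorbed. At 60 per arm, raw power is 94% at SD 28.7 and 91.5% at SD 30. This also stands, but the plan's own power claim is for 40 per arm and treats the other 60 as lost.

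**The authors may have meant a change-score test.** Section 7.4.3 does not use the word unadjusted, and 7.4.1 plans on change. But 7.4.3 tests the primary outcome, and two sections define that as the 30-minute score. Either reading requires an edit.

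**The baseline ambiguity is small.** The verbal score in 7.3.2 is explicitly the screening score, and a 0-minute nausea level is also collected. What remains open is whether the VAS precedes the drink, a matter of minutes because inhalation is to start within 5 minutes of the solution. That is fair. It is a clarification, needed because the repair depends on it.

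**Conclusion.** The inconsistency is real and should be fixed. It does not invalidate the trial. The 40 per arm is correct for a change-score test and unsupported for the raw-score test that is planned. The direction of the power error cannot be determined from the documents. At the planned change SD, raw-score power across the assumed settings is 75.5% to 92%, against 83% to 94% with baseline adjustment. These ranges rest on the assumed baseline SDs and correlations; the break-even SD of about 28.5 mm at 40 per arm does not. Adjustment gains appreciable precision over the raw test only when baseline and 30-minute scores are appreciably correlated, and it does not protect against a change SD above 28.7 mm.

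**What to change.** - **Section 7.4.3:** make the primary analysis a linear model of 30-minute nausea VAS on arm, with baseline nausea VAS as covariate. Report the adjusted mean difference with a 97.5% CI for each primary comparison. Name those comparisons, since 7.4.1 divides alpha over two hypotheses and section 6 states one. Keep the unadjusted t test as a sensitivity analysis. If the multiple regression has further covariates, list them in advance and label it supportive.
- **Sections 7.3, 7.3.2 and the schedule table:** define baseline as the nausea VAS marked before the oral solution, and make all three places agree.
- **Section 7.4.1:** state that if the change SD is 28.7 mm, the residual SD of this model cannot exceed it, so 40 per arm gives about 79–80% power or more.

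Two other routes would also reconcile the sections: test the change score in 7.4.3, or give a sourced SD for the 30-minute score in 7.4.1 and recompute. Baseline adjustment is preferable because, apart from one degree of freedom, it is at least as precise as the change score.

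**Cost:** a few sentences, one degree of freedom and, if the 0-minute VAS would otherwise follow the drink, one VAS mark before it. No extra patients.

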study conclusion the patient's provider will be asked to indicate his/her belief as to whether the pad was a treatment or placebo and whether the oral solution was a treatment or placebo. Other data collected will include times and doses for all medications (including preparation pads) and fluids administered, episodes of vomiting (defined as forceful expulsion of gastric contents separated by at least 2 minutes), disposition (admission versus discharge), final clinical impression at the time of disposition, and time to disposition. Subjects will be followed and data collected for the entirety of their ED stay. A lockbox identified as "Nausea study" will be maintained in the ED for data collection form storage to which only the investigators and ED staff will have the key. ISO prep pads, saline prep pads, Ondansetron oral solution, and its matching placebo do not require storage in a hazardous material cabinet. This study will be registered on ClinicalTrials.gov.

Subjects will comprise a convenience sample. Study investigators will log hours of recruitment on a password-protected excel spreadsheet which will not contain any PHI. To confirm the sample is representative of all patients presenting to the ED with nausea, we will examine CHCS ad hoc data already generated by the ED on a routine basis for performance improvement purposes for all patients whose registration chief complaint contains either the words "nausea" or "vomiting" including patients not enrolled in our study. Comparison of the characteristics of enrolled patients with patients not enrolled will enable us to establish whether there was selection bias in our study. These patients' FMP prefix and sponsor last 4 will be cross-referenced against our enrolled subjects. With our enrolled subjects removed, we will extract only the following data: age, sex, ESI category, diagnoses, receipt of any anti-emetics to include drugs and doses, and whether or not admitted. Any patient on the Ad Hoc list who is 89 or older will be recorded as ≥89. We will also need to access cross-reference the SSN or MRN of all these patients along with the dates of treatment data to establish whether a given CHCS data point represents a visit from a patients recruited into the study or a non-recruited patient. No PHI will be extracted from the ad hoc data. These extracted data will be maintained on a password-protected, CAC-enabled government laptop.

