76 provided by the study investigator. Reports for events determined by either the investigator or research monitor to be
77 possibly or definitely related to participation and reports of events resulting in death will be promptly forwarded to the
78 RHC-C IRB office.
79
80

81 **10.0 WITHDRAWAL FROM STUDY PARTICIPATION.** Patients may withdraw their consent at any time and
82 discontinue further participation in this study without affecting their eligibility for care or any other benefits to
83 which they are entitled. They may withdraw for any reason. Should they choose to withdraw, they must notify
84 the principle investigator or any other member of the research team. They may do this during the study in
85 person by verbally stating to the research team member that they wish to withdraw. After the study, they may
86 withdraw by calling or writing the principle investigator (PI contact information provided to all study participants
87 on the informed consent document). We will analyze any data collected on these patients prior to withdrawal unless
88 requested by the subject to destroy their data form. There are no risks associated with withdrawing from the study.
89

90 **11.0 USAMRMC Volunteer Registry Database.** N/A
91

92 **12.0 REFERENCES.**

5. Pellegrini J, et al. Comparison of inhalation of isopropyl alcohol vs promethazine in the treatment of postoperative nausea and vomiting (PONV) in patients identified as at high risk for developing PONV. *AANA J* 2009;77:293-9.
6. Winston AW, et al. Comparison of inhaled isopropyl alcohol and intravenous ondansetron for treatment of postoperative nausea. *AANA J* 2003; 71:127-32.

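### Section 7.4.3 has no rule for a missing 30-minute VAS and leaves the recorded earlier scores out of its t test; the likely bias is small, and the surer loss is precision

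*Combined protocol and SAP*

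**What the plan says.** Section 7.4.2: "Primary outcome is nausea VAS measurement" at 30 minutes, a single time point. Section 7.4.3: "the primary outcome will be evaluated using a two-tailed independent sample student t test". It continues: "The primary outcome will further be evaluated using a multiple regression model". The covariates are not named, and neither this section nor any other gives an analysis population, a missing-data rule or a sensitivity analysis.

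Section 7.4.1 sets 60 of 180 subjects against "Estimate Participant Drop Out / Withdrawal", without saying when these losses are expected. Section 6 says "Subjects will be followed and data collected for the entirety of their ED stay".

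Section 10.0, on subjects who withdraw, says "We will analyze any data collected on these patients prior to withdrawal unless" and makes one exception, where this is "requested by the subject to destroy their data form".

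Early scores exist. Besides the 30-minute reading, Section 6 says nausea measurements "will also be collected at 10, 20, 40, 50, and 60 minutes, and then every hour up to 5 hours". Section 7.3 has a shorter list, but it too includes 0, 10, 20 and 30 minutes. Section 7.4.3 assigns no test to the 10- and 20-minute scores.

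**The concern.** A t test on the 30-minute score needs that score, and an ordinary regression with it as outcome drops every row that lacks it. A subject who leaves at, say, 25 minutes with three scores on file would therefore contribute nothing to the primary analysis, and 7.4.3 offers no way to keep the undertaking in Section 10.0 for that subject's nausea scores.

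Loss related to nausea is plausible. Section 8.1 presents withdrawal as one safeguard when the allocated treatment does not work, although a subject may instead ask for an antiemetic and stay in the study. Follow-up also ends at disposition (Section 7.3), so an early disposition is a second route to a missing value. If those who leave feel worse than those who stay, the completers' means are too low, and the arm difference is wrong unless the distortion is equal in both arms.

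Without a written rule, the handling would be chosen after the data are seen, in a trial where Section 6 itself expects difficulty in blinding to scent. Separately, a t test on the 30-minute score alone discards the information in the time-0 score, even with no loss at all.

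**Working it through.** **1. The plan's own figure.** Inputs from Section 7.4.1: difference 20 mm, SD 28.7, two-sided alpha 0.025, power 0.80.

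n per arm = 2 × [28.7 × (2.241 + 0.842) / 20]² = 39.1, so 40. This agrees with the plan. A t-based calculation gives 40.4. The allowance also agrees: 120 / (1 − 60/180) = 180.

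**2. What the allowance protects.** If all 60 lack a 30-minute score, 40 per arm remain and power is 80.9% (normal) or 79.5% (t). With no loss, 60 per arm give 94.2% or 93.8%. Over-enrolment protects power. It does nothing about selective loss.

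**3. Bias when incomplete subjects are dropped.** In each arm let f be the fraction without a 30-minute score and D the amount by which their mean would exceed that of the completers. Then

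observed difference = true difference − (f_worse × D_worse − f_better × D_better).

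Neither f nor D is in the documents, so the values below are assumptions.
- Equal f and equal D: bias 0.
- f = 33% in the worse arm and 20% in the better, D = 10 to 30 mm: too small by 0.133 × D = 1.3 to 4.0 mm.
- f = 10% in both arms, D = 20 mm in the better arm only: 20 + 0.10 × 20 = 22 mm, too large by 2 mm. With no true difference the same pattern gives 2 mm instead of 0.

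The sign therefore depends on whether the arms share one loss mechanism.

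**4. Illustration with a common mechanism.** Assumed: 60 per arm; scores held to 0-100 mm; mean 58.6 at time 0; means 48.2 and 28.2 at 30 minutes (true difference 20.0); SD of change averaging 28.7; correlation 0.50 over 30 minutes before the scale limits are applied. Loss is split equally over 0-10, 10-20 and 20-30 minutes and follows the last recorded score, at log-odds 0.25 / 0.5 per 10 mm (odds ratio 2.0 / 4.2 per 28.7 mm). Mean estimates in mm:

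| Lost before 30 min | t test | time-0 adjusted | repeated measures |
|---|---|---|---|
| 5% | 19.8 / 19.6 | 19.9 / 19.7 | 19.9 / 19.9 |
| 10% | 19.6 / 19.1 | 19.7 / 19.4 | 19.9 / 19.8 |
| 20% | 19.2 / 18.1 | 19.4 / 18.7 | 19.7 / 19.5 |
| 33% (all 60) | 18.5 / 16.8 | 18.9 / 17.6 | 19.5 / 19.3 |

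The t test falls short by 0.4 to 0.9 mm at 10% (under 0.2 standard errors) and by 1.5 to 3.2 mm at 33% (1.5/5.87 = 0.25 to 3.2/5.53 = 0.6 standard errors). With no true difference and this common mechanism (slope 0.5), its mean stays within about 0.3 mm of zero.

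**5. Where the early scores help less.** If all loss is before 10 minutes and follows the time-0 score, the t test and the model agree within 0.1 mm. If the unseen 30-minute score drives loss, both are low: t test 19.0 / 17.5 and model 19.4 / 18.4 at 10%; 16.5 / 12.7 and 17.7 / 14.8 at 33%.

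**6. Precision under random loss.** At 10% loss the standard error is 5.23 mm (t test), 4.62-4.65 (time-0 adjusted) and 4.56-4.58 (repeated measures). At 33% it is 6.19, 5.45 and 5.17. Adjustment at 10% cuts the variance by 1 − (4.62/5.23)² = 22%.

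The gain depends on the correlation ρ between the time-0 and 30-minute scores, which the documents do not give. By the approximation SE × √(1 − ρ²), 5.23 becomes 4.99 at ρ = 0.3, 4.53 at 0.5 and 3.73 at 0.7. The simulated gain is slightly below the 0.5 figure because the scale limits weaken the correlation.

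**The case against.** The best defence is that little is at stake. At 10% loss following recorded scores, the t test moves by less than 1 mm against a 20 mm target. Subjects are in the ED throughout, can ask for an antiemetic without withdrawing, and need only reach half an hour. This stands.

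Nor is Section 10.0 broken for everyone who withdraws. A subject who leaves after 30 minutes has the primary value, and a rescue antiemetic received before leaving can enter the chi-squared test. The gap concerns mainly nausea scores of subjects who leave before 30 minutes. This also stands.

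A regression is already planned, and naming time-0 VAS as its covariate would bring most of the precision gain. That is right, so adjustment is the main request and the repeated-measures step a preference. One could also read 7.4.1, which uses the SD of change, as implying a t test on change. Section 7.4.2 defines the outcome as the score itself, and a change-score test, though nearly unbiased in the illustration (19.5 / 19.1 at 33%), has a standard error of 6.3 mm against 5.0-5.1 for the model.

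The illustration does not impose the entry threshold of 3 on the VNRS. Removing time-0 scores below 30 mm cuts the largest t-test bias in the table from about 3.4 mm (in a separate run) to 2.5 mm.

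Three stronger readings are tempting and not supported:
- That the plan chose a complete-case analysis. It is silent; omission follows only from running the named tests as they stand.
- That a third of subjects will lack the primary value. The 60 is an allowance over the whole ED stay, with no timing.
- That the t test would manufacture a benefit. Under a common loss mechanism it has almost no bias when there is no true difference. Step 3 shows that this protection fails if the mechanisms differ by arm, but nothing in the documents says that they do.

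**Conclusion.** The point holds as an omission with a cheap improvement attached. It is not an error in a figure: 40 per arm and 180 in total are consistent with the stated inputs. How many subjects will lack a 30-minute score cannot be known from the documents.

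The sizes in step 4 rest on loss that follows recorded nausea in the same way in both arms. Loss driven by the unseen score would bias the t test more (1.0 to 2.5 mm at 10%), and arm-specific loss could inflate the difference. The precision gain from time-0 adjustment needs no assumption that loss is selective, only a useful correlation with the 30-minute score. The repeated-measures model adds little precision at low loss. Its value is that subjects who leave between 10 and 30 minutes contribute, and that it removes most of the bias in step 4. The change should be made, but the trial does not fail without it.

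**What to change.** In Section 7.4.3:
- For each planned comparison, at the 0.025 level of 7.4.1, make the main estimate of the 30-minute arm difference one adjusted for time-0 VAS. Preferably take it from a likelihood-based model of the 10-, 20- and 30-minute VAS with arm-by-time terms, time-0 VAS by time and unstructured covariance. Keep the t test as a supporting analysis.
- State that all randomised subjects are analysed as allocated, give the rule for a missing 30-minute score, and reconcile both with Section 10.0, including forms destroyed on request.
- Tabulate missing 30-minute scores and destroyed forms by arm, with time of leaving and reason where known.
- Add one sensitivity analysis that imputes missing 30-minute scores, includes subjects with only a time-0 score, and shifts the imputed values over a stated range, for example 0 to 20 mm worse, by arm. For scale: in the 33% row at the steeper slope, 38.5% and 28.3% are missing in the worse and better arms. A 10 mm shift in both arms moves the difference by 10 × (0.385 − 0.283) = 1.0 mm; in the worse arm only, by 3.9 mm.

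The cost is protocol wording and slightly more analysis work; the scores are already collected and the sample size does not change. The main model assumes that the observed scores explain the loss, and it recovers nothing for subjects who leave before 10 minutes, so the sensitivity analysis must include them.
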